### **Open-Label Extension Period (OLEX)**

Injection Visit (V6, V10, V14): Day 1 of the 2nd to 4th treatment cycle.

Telephone Contact  
(TC2, TC3, TC4): Day 8 (Week 1)  $\pm$  3 days of 2nd to 4th treatment cycle.

Ctrl. Visit (V7, V11, V15): Day 29 (Week 4)  $\pm$  3 days of 2nd to 4th treatment cycle

Ctrl. Visit (V8, V12, V16): Day 57 (Week 8)  $\pm$  3 days of 2nd to 4th treatment cycle

End of Cycle Visit (V9, V13) Day 99 (Week 14)  $\pm$  14 days of 2nd and 3rd treatment cycle

End of Study Visit (V17): Day 99 (Week 14)  $\pm$  14 days of 4th treatment cycle.

### **Revisit for reinjection**

If any eligibility criterion is not met either at the Final Visit of MP (V5) or at an End of Cycle Visit in OLEX (V9 or V13), the injection may be rescheduled within up to 16 weeks after the last injection treatment. An injection visit may be rescheduled ('revisit'), if the investigator assumes that the respective eligibility criterion is likely to be fulfilled within the remaining period of time to complete 16 weeks after the last injection treatment. For details on eligibility criteria see [Section 7.3.1](#).

If the investigator assumes the criterion will not be met within up to 16 weeks after the last injection treatment, or if the subject does not fulfill all eligibility criteria at the rescheduled injection visit, the subject will be withdrawn from the study (see [Section 7.4.1](#)). A subject can perform only one revisit, i.e., the revisit cannot be repeated even if the limit of 16 weeks after the last injection has not been reached.

If rescheduling of an injection visit becomes necessary, this additional visit will be interposed into the regular visit series without affecting the numbering or time window of regular visits, i.e., the day of injection is designated as Day 1 of each cycle. If an End of Cycle Visit and an Injection Visit should not be performed on the same day (e.g., if a revisit is required), all procedures that would be transferred from the End of Cycle Visit to the Injection Visit must be performed again at the revisit. At a rescheduled injection visit (after eligibility criteria have been confirmed and before injection), AEs/AESIs, vital signs, concomitant medication, and efficacy assessments will be documented.

### **AESI monitoring and Safety Visit**

To monitor potential spread of toxin, the subject (if applicable) and/or parent(s) or caregivers (if applicable) will be actively questioned for the occurrence of AESIs at each visit or Telephone Contact [TC] starting with Baseline Visit of MP (V2). If a TC identifies an (S)AE/AESI that needs confirmation or treatment (e.g., respiratory disorder, dyspnoea, aspiration, dysphagia, speech disorder, dysphonia, other signs of bulbar palsy or botulism), the investigator must schedule a Safety Visit [SV] in addition to scheduled visits as soon as possible after the Telephone Contact. SV are unscheduled extra visits for assessment of (S)AE/AESIs only.

[figure not shown]
If a subject withdraws from participation during the study at any point of time, every attempt should be made to conduct the assessments foreseen for the End of Study Visit (V17).

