## 7.3 Removal of subjects from treatment or assessment

### 7.3.1 *Discontinuation of subjects*

In accordance with the Declaration of Helsinki and the IC form, the subject or parent(s) may discontinue the study at any time without any penalty or loss of benefits to which the subjects is otherwise entitled (see [Section 7.4.3](#)). Both the discontinuation of study and the reason(s) why the study was prematurely discontinued must be recorded in the subject's file and the eCRF. Date and discontinuation circumstances should be stated. Further details on discontinuation could be documented in the respective section of the "End of Study" form of the eCRF.

Subjects must be discontinued from the study by the investigator at any time for any of the following reasons:

- Withdrawal of IC.
- Treatment with any other IP in another clinical study.
- Treatment with any BoNT other than study medication.
- Pregnancy (no further administration of IP(s), blood draw, or any other interventional procedure will be performed; see [Section 10.4](#)).
- Any AE for which treatment continuation would constitute an unacceptably high risk for the subject.
- AESIs of severe intensity that represent respiratory function disorders or swallowing disorders will trigger the premature termination of a subject without re-exposition to IP. The terms for these severe AESIs are:
  - AESI terms related to respiratory function disorders are aspiration, diaphragmatic paralysis, dyspnoea, pneumonia aspiration, respiratory arrest, respiratory depression, and respiratory failure.
  - AESI terms related to swallowing disorders are bulbar palsy, multiple cranial nerve palsies, dysphagia, hypoglossal nerve paresis, cranial nerve paresis, cranial nerve paralysis.
- Injection treatment cannot be performed for any reason, not even with local anesthesia and/or analgosedation.
- Eligibility criteria are not met after the previous injection of IP in the respective treatment cycle (MP or OLEX) (see [Section 7.3.1](#)).

The DMC may recommend further criteria for discontinuation. Deviations from this study protocol, or conditions comprising exclusion criteria established in [Section 7.3](#) that arise after the subject has been included in the study may (but will not necessarily) lead to the discontinuation of subject's study participation. All such conditions must be properly documented.

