Any subject who discontinues from the study due to AEs will be treated according to standard clinical strategies. All pertinent information concerning the AE will be documented in the subject's file as well as in the eCRF AE report form (and in addition in an SAE or AESI report form, if applicable).

Following discontinuation, a final examination (End of Study Visit) should be performed for safety reasons. However in a pregnant female no invasive assessments, e.g., blood sampling should be performed. The pregnancy has to be followed up until the date of delivery (see also [Section 10.4](#)). The investigator is required to make every effort to contact the subject (if applicable) or parent(s) lost to follow-up, and all such efforts should be documented in the subject's file (e.g., times and dates of telephone contact, copies of letters).

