#### 9.1.1 *Clinical evaluations*

At the beginning of the study, information such as the subject's medical history, all past and concomitant medications within the last 4 weeks, phenol and alcohol injections within the last 6 months and BoNT medication regardless the time of administration prior to the Screening Visit will be recorded from the subject's file or from information given by the subject (if applicable) and the parent(s) ([Section 8.3](#)). Other data will be collected as required, including information obtained from physical and neurological examinations. The GMFCS level will be assessed as described in [Appendix 16.8](#). A review of this information will allow the investigator to assess whether the subject should be enrolled at the Screening Visit. Other screening data will be collected at the Baseline Injection Visit before decision for eligibility and randomization.

Instructions regarding assessments on the scales will be provided in a manual for investigators and will be trained at the investigators' meeting(s) before study start. The same investigator must perform the ratings on the AS at Baseline Injection Visit and Control Visit at Week 4 in MP. Also at all other site visits this investigator should preferably perform the AS ratings to reduce variability of assessments. Preferably the same investigator should interview the subject (if applicable) and the parent at all visits. Preferably, the same parent(s) or caregiver (if applicable) should rate on scales at all visits. Preferentially, all study visits are performed at a similar day time throughout the study to reduce variability of assessments.

---

 In subjects, living e.g. in a special-care unit permanently or most of the time with caregivers being his/her main social contacts, a caregiver may replace parent(s) for the assessment of the respective scales and measures,

Rating on the Investigator's GICS at Control Visit V3 must be performed by the same investigator, who had performed clinical assessment and evaluation of the subject at the Baseline Injection Visit V2.

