#### 9.1.1.2 Global Impression of Change Scales (GICS)

The Global Impression of Change Scales (GICS) are subjective global outcomes to assess independently the investigator's, child's/adolescent's, and parent's or caregiver's (if applicable) impression of change due to treatment. Caregiver(s) may substitute parent(s) for the assessment of GICS, if they are main social contacts of subjects, e.g. in a special-care home.

At Week 4 of each treatment cycle in MP [REDACTED] the investigator, child/adolescent (if applicable), and parent(s) or caregiver (if applicable) evaluate the global change of spasticity separately in UL and LL (if applicable). The GICS will be provided in local language.

Since the Investigator's GICS is based on the clinical impression of the change due to treatment of the subject's spasticity compared to the condition before the last injection, the same investigator, who has performed clinical assessments at the Baseline Injection Visit V2 of MP must rate on this scale at Control. Visit V3 at Week 4 of MP. [REDACTED]

All assessments of GICS will be made before AS assessments in order not to be confounded by these assessments.

The question of the GICS for the investigator is:

‘Based on your clinical experience, what is your overall impression of change of the subject’s upper/lower limb spasticity due to treatment, compared to the condition before the last injection?’

Please check the one option that best fits your overall impression of change.’

For the GICS versions for child/adolescent and parent(s)/caregiver please refer to [Appendix 16.3](#). For children/adolescents and parent(s) or caregivers who are not willing or able to the self-assessment, the respective GICS versions will not be assessed. If children/adolescents can not self-complete the questionnaire due to e.g. motor abilities, the clinical staff can ask the GICS. Only one score for parent(s) or caregiver will be recorded in the eCRF even when more than one parent or caregiver is present at study visits. Therefore, parents/caregivers have to agree on the assessment or the assessment has to be delegated to one person.

The response option for all GICS versions is a common 7-point Likert scale that ranges from -3 = very much worse to +3 = very much improved:

- +3  Very much improved
- +2  Much improved
- +1  Minimally improved
- 0  No change
- 1  Minimally worse
- 2  Much worse
- 3  Very much worse

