In order to investigate the impact of missing values and different approaches for imputation, further sensitivity analyses will be performed on the PPS as well as on the FAS of the MP using the LOCF principle and without missing replacement (observed case analysis). For this purpose the statistical model as described above but without visit*treatment as interaction and without visit as repeated factor will be applied for LOCF analysis and for observed case analysis. Since there is no assessment of AS between baseline and V3, the baseline observation will be carried forward to Week 4 equals the LOCF analysis. Therefore the LOCF method is equivalent to the baseline observation carried forward (BOCF) method in this special case. The following SAS code will be used:

```
proc mixed data = dataset;  
  class treatment site btx;  
  model AS_change_wk4 = treatment site btx AS_baseline GMFCS / solution  
    ddfm=kr;  
  lsmeans treatment / pdiff CL alpha=0.05;  
run;
```

Further, a non-parametric Wilcoxon rank-sum test will be performed as sensitivity analysis of the primary efficacy variable to investigate the impact of potential deviations from the assumption of normal distribution (for FAS of the MP and PPS subset, using LOCF). The following working hypotheses will be tested:

H₀: Prob. distributions for high dose group and low dose group are identical

vs.

H₁: Prob. distribution for high dose group shifted to right or left of distribution for low dose group.

The Wilcoxon rank-sum test will be performed by use of the following SAS code:

```
proc npar1way data=dataset wilcoxon;  
  class treatment;  
  var AS_change_wk4;  
  exact;
```

run;

Furthermore, descriptive summary statistics, shift tables and frequency tables of changes will be given for the primary efficacy variable.

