7.1.2 Co-Primary, Key-Secondary and Secondary Efficacy Variables

Co-primary efficacy variable:

1. Step: Both, the primary efficacy variable and the co-primary efficacy variable have to show statistically significant treatment differences in order to prove superiority of high dose vs. low dose treatment. No α -adjustment for multiplicity is necessary.

The co-primary efficacy variable is the Investigator's Global Impression of Change Scales (GICS) for upper limb at Day 29 (Week 4) of MP. As for the primary efficacy variable, an analysis of covariance (ANCOVA) approach (2-sided, significance level $\alpha=0.05$) with comparison of least square means will be used for the confirmatory analysis of the co-primary efficacy variable. The dependent variable is defined as the 'Investigator's GICS at Day 29 (Week 4) for upper limb of MP'. The independent variables are defined as treatment group (high dose, low dose), pooled sites, BoNT-A pre-treatment status (pre-treated, treatment naïve) as fixed factors and the covariates are the maximum AS score of the two possible primary target clinical patterns flexed elbow or flexed wrist at baseline (Day 1 of MP) and the GMFCS-E&R level at Screening Visit. The following SAS code will be used:

```
proc mixed data = dataset;  
  class treatment site btx;  
  model I_GICS_wk4 = treatment site btx max_AS_baseline GMFCS / solution;  
  lsmeans treatment / pdiff CL alpha=0.05;  
run;
```

Positive values for differences between least square mean estimates as defined by the working hypotheses (see primary efficacy variable) thereby indicate better results (higher GICS values at Day 29, Week 4) in the high dose group as compared to the low dose group. Confirmatory testing will be performed on the FAS of MP with replacement of missing data, setting all missing values of the co-primary efficacy variable to "0" (no change).

Further sensitivity analyses will be performed on the PPS as well as on the FAS of the MP and the PPS without missing replacement (observed case analysis).

Further, a non-parametric Wilcoxon rank-sum test will be performed as sensitivity analysis to investigate the impact of potential deviations from the assumption of normal distribution (for FAS and PPS subset, imputing missing data by "0", i.e. no change). The same SAS code as for the primary efficacy variable will be used with primary efficacy variable replaced by co-primary efficacy variable.

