4. Step: Only if the confirmatory analysis of step 3 yields a statistically significant result, in a fourth step, using a hierarchical testing approach, the mid dose treatment will be compared to low dose treatment for the primary efficacy variables and the co-primary efficacy variable. The analysis models will be identical to the analyses described above for the 1st step replacing high dose group with mid dose group. Both, the primary efficacy variable and the co-primary efficacy variable have to show statistically significant treatment differences in order to prove superiority of mid dose vs. low dose treatment.

For the confirmatory analyses a two-sided significance level of $\alpha=0.05$ will be applied and analysis models as described for the (co)-primary efficacy variables will be applied. The

analysis of the primary efficacy variable and of both key-secondary efficacy variables will be performed on the FAS of the MP with an MMRM approach. For the co-primary efficacy variable and the co-primary variable restricted to the subpopulation, missing data will be imputed by "0", i.e. no change.

All other test procedures will be explorative. Sensitivity analyses will be performed on the PPS of MP using the MMRM approach, as well as on the FAS and the PPS of MP using a mixed model approach without repeated measures first with the LOCF principle and second without replacement of missing values (i.e., observed case analysis). As the GICS is measured at Control Visit V3 only it is not possible to apply a model based analysis like mixed model repeated measurement.

Secondary efficacy variables:

All secondary variables will be analyzed on the FAS of the MP and the PPS. All tests will be descriptive and interpreted in an explorative manner. Treatment comparisons will be tested for comparison of the high versus low dose treatment group and the mid versus low dose treatment group, respectively.

Ashworth scale of the UL

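### A child who discontinues before Week 4 is sent to assessments that do not include the co-primary GICS, so an avoidable zero enters the confirmatory test; the likely effect is small

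*Protocol*

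**What the plan says.** **Withdrawal visit.** Protocol 6.1 (AESI monitoring and Safety Visit) directs that on withdrawal at any time "every attempt should be made to conduct the assessments foreseen for the End of Study Visit (V17". Protocol 7.3.1 gives the purpose: "Following discontinuation, a final examination (End of Study Visit) should be performed for safety reasons". The same section lists mandatory reasons for discontinuation, for example "AESIs of severe intensity that represent respiratory function disorders or swallowing disorders will trigger the premature termination of a subject".

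**GICS timing.** Protocol 9.1.1.2 schedules the scale "At Week 4 of each treatment cycle in MP". SAP 7.1.2 confirms a single main-period rating: "As the GICS is measured at Control Visit V3 only it is not possible to apply a model based analysis". SAP 8 places the extension-period ratings at V7, V11 and V15, so V17 is not a GICS visit.

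**Missing co-primary value.** The confirmatory ANCOVA in SAP 7.1.2 is run after "setting all missing values of the co-primary efficacy variable to" zero, meaning no change. SAP 7.7.1 calls this conservative on the assumption that the percentage missing is similar in the three arms.

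**Missing Ashworth score.** The confirmatory MMRM imputes nothing (SAP 7.7.1). For the LOCF sensitivity analysis, SAP 7.1.1 says "Since there is no assessment of AS between baseline and V3, the baseline observation will be carried forward to Week 4", and Protocol 12.4.7.1 likewise carries baseline to Day 29. SAP 7.7.1 instead carries forward the last observation, with baseline counted as one.

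**FAS.** A baseline Ashworth score in either main pattern is enough for entry (SAP 5). SAP 7.1 sets the estimand as the effect in all FAS subjects of the main period.

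**The concern.** The compared exposure is complete once the V2 injection has been given. The next possible injection is at V6, at least 12 weeks later. A child who discontinues on, say, Day 20 is therefore as informative about the Week 4 effect as one who stays, provided someone rates the outcome. The plan asks for a visit but does not schedule the co-primary rating at it, and then fills the gap with 0.

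That zero goes into the confirmatory test, in Step 1 and again in the GICS tests of Steps 2 and 4. If early discontinuation depends on dose, through severe toxin-spread events or lack of effect, the zeros fall unevenly across arms and the SAP's condition for calling them conservative fails. The same child, lacking any V3 to V5 Ashworth score, drops out of the primary model although the estimand includes the whole FAS.

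The protocol already follows children after treatment stops in one situation: Protocol 10.4 keeps a subject who becomes pregnant after V2 in the applicable visits until the cycle ends. Protocol 6.1 and 7.3.1 make no such provision for the other reasons.

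**Working it through.** **Inputs (SAP 4).** Arms of 172, 86 and 86; two-sided alpha 0.05. Ashworth mean changes -1.01 and -0.70, SD 0.6. GICS means 1.4 and 0.8, SD 1. Missing rate 3%.

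**Step 1: reproduce the plan.** Setting 3% to no change gives 0.97 × (-1.01) = -0.98 and 0.97 × (-0.70) = -0.68 for Ashworth, and 0.97 × 0.60 = 0.582 for GICS. These are the SAP's figures. Two-sample t-test power (noncentral t):

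| Comparison | Ashworth (0.30, SD 0.6) | GICS (0.582, SD 1) | Product | SAP |
|---|---|---|---|---|
| High vs low | 96.5% | 99.2% | 95.8% | 96.5 / 99.2 / 95.7% |
| Mid vs low | 90.3% | 96.7% | 87.3% | 90.3 / 96.7 / 87.3% |

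**Step 2: how many children.** 0.03 × 344 = 10.3 in total: 0.03 × 172 = 5.2 in the high arm and 0.03 × 86 = 2.6 in each of the others. This is missingness from all causes. Children who leave before V3 and could still be assessed are an unknown subset.

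**Step 3: what equal loss costs in power.** Compare no loss (differences 0.31 and 0.60) with 3% loss handled as planned (Ashworth dropped from the model, GICS set to 0):

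| Comparison | Joint power, no loss | Joint power, 3% loss | Gap (points) |
|---|---|---|---|
| High vs low | 96.9% | 96.2% | 0.7 |
| Mid vs low | 89.7% | 88.1% | 1.6 |

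**Step 4: unequal loss.** The rates are assumptions; the documents give none by arm. With mH and mL the proportions missing in the high and low arms:

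- GICS difference = 1.4 × (1 - mH) - 0.8 × (1 - mL)
- Ashworth difference with baseline carried forward (sensitivity analysis only) = 1.01 × (1 - mH) - 0.70 × (1 - mL)

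| mH, mL | GICS difference | Change from 0.600 | Ashworth difference |
|---|---|---|---|
| 3%, 3% | 0.582 | -3% | 0.301 |
| 6%, 1% | 1.316 - 0.792 = 0.524 | -13% | 0.949 - 0.693 = 0.256 |
| 1%, 6% | 1.386 - 0.752 = 0.634 | +6% | 1.000 - 0.658 = 0.342 |
| 6%, 0% | 0.516 | -14% | 0.249 |
| 0%, 6% | 0.648 | +8% | 0.352 |

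At 6% and 0%, GICS power is 97.3% and the power of the carried-forward Ashworth analysis is 88.0%. If the true GICS means were both 0.8, a 6-point imbalance would shift the difference by 0.8 × 0.06 = 0.048 and raise the two-sided rejection rate of that single test from 5.0% to about 6.5%.

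**Step 5: the LOCF texts side by side.** SAP 7.1.1 and Protocol 12.4.7.1 put baseline at Week 4. SAP 7.7.1 puts the last observation there. The two agree for scheduled visits, because the only scheduled contact between V2 and V3 is a telephone call. They differ for a child with an Ashworth score at an early withdrawal visit: the first gives a change of 0, the second the observed change. The visible SAP has no window or mapping rule for such a visit.

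**The case against.** **What stands.** The procedures at V17 belong in Protocol Tables 16 and 17, whose content is not shown in the public text, so an instruction for early termination could sit there. That an Ashworth score is taken at the withdrawal visit is an inference from Protocol 9.1.1: "Also at all other site visits this investigator should preferably perform the AS ratings". That sentence says who should rate and is not an assessment schedule. The 3% loss with no-change imputation is already built into the sample size for both outcomes, and observed-case analyses are pre-specified for both. Step 1 needs both outcomes to be significant, so a GICS difference inflated by zeros cannot carry it alone.

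Direction matters too. Severe adverse events would plausibly remove more high-dose children, which shrinks the difference. The anti-conservative case needs more low-dose children to leave early, although leaving forfeits three open-label cycles at the high dose.

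**What does not remove the point.** The visible text places the GICS only at Week 4 visits in three separate places. Observed-case analysis shows what happens without the zeros but does not recover a rating that could have been made. The similar-missingness condition is stated in the SAP and not secured by anything in the design.

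**Stronger readings that the documents do not support.** A reader might infer that the SAP ignores an Ashworth score that was actually taken. But the score itself is only inferred, and SAP 7.7.1, read literally, would use it in LOCF, so the fault is a missing rule and two conflicting sentences. A reader might also infer that both primary outcomes are set to no change in the confirmatory analysis. Only the GICS is; the Ashworth score is left unimputed there, and its no-change version appears only in a sensitivity analysis.

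**Conclusion.** The gap is real and avoidable, and its likely effect is small. By the visible text, a child discontinued after V2 and before V3 has no scheduled co-primary rating, receives a zero in the confirmatory test, and adds nothing to the primary MMRM while counted in the FAS. The Ashworth LOCF rules conflict for any such child who has an early score.

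At the planned 3%, equal across arms, the GICS difference falls by 0.018 and the joint power by at most 0.7 points (high vs low) or 1.6 points (mid vs low). The stated power is not undermined. The remaining risk is bias from dose-related early discontinuation: between -13% and +6% of the GICS difference at assumed losses of 6% and 1%. Those rates have no source in the documents, and they treat every lost child as recoverable, which overstates what a change could gain. The conclusion also assumes that the activity tables do not add a GICS rating at early termination. This is a worthwhile low-cost improvement and not a threat to the trial's conclusions.

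**What to change.** **Protocol 6.1 and 7.3.1.** State that, unless follow-up is refused, a child discontinued after V2 and before V3 keeps the Day 29 visit for two ratings: the Ashworth score of the primary pattern and the Investigator's upper-limb GICS. If Day 29 is not possible, both are rated at the early visit. The existing discontinuation criteria and treatment rules stay exactly as they are; this concerns data collection only.

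**SAP 7.1.1, 7.1.2 and 7.7.1.** Use early-visit values only in pre-specified sensitivity analyses: LOCF for the Ashworth score, and a GICS analysis with the early rating in place of 0. Do not put them into the confirmatory MMRM, because a score taken before Day 29 is not a Week 4 value.

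**LOCF wording.** Align SAP 7.1.1 and Protocol 12.4.7.1 with SAP 7.7.1, so that baseline is carried forward only where no later Ashworth score exists.

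**Cost.** A few sentences, one retained visit for a few children, and one added sensitivity analysis. The downside is that early ratings are mistimed, which is why they stay out of the confirmatory analysis.
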